2.5.2 Statistical hypothesis, model, and method of analysis

Part 1: Selection Phase

No formal hypothesis testing will be conducted in part 1. The objective of this part of the study is to explore the anti-tumor activity of the combination of spartalizumab with LAG525 agent in subjects with LAG-3 positive melanoma as measured by ORR per RECIST v1.1, and to expand this new arm if it shows promising efficacy.

To determine whether the arm has the potential to demonstrate clinically meaningful response rate, a specific efficacy probabilistic threshold should be met during the selection phase to advance to the expansion phase. If not, the arm will be declared as futile and won’t be expanded. These thresholds and probabilities are highlighted in [Table 2-2](#).

Table 2-2 Probabilities thresholds used to declare efficacy or futility for arm 1A

Decision rule	Action
$P(\text{ORR} \geq 20\%) \leq 70\%$	Drop arm for futility
$P(\text{ORR} \geq 20\%) > 70\%$	Efficacy signal - Consider advancing arm to expansion phase (part 2)

To calculate the posterior probabilities, a beta-binomial posterior distribution will be used as shown below:

$$p \sim \text{beta}(y + 1, n - y + 1)$$

Where y is the number of confirmed responses in arm 1A and n is the number of subjects treated. In calculation of the posterior distribution, uninformed prior Beta[1,1] will be taken into account. The posterior probability will be calculated based on the observed ORR using RECIST v1.1 criteria at interim analysis.

The final decision on whether the arm will be selected for advancement to the expansion phase will primarily be based on the observed ORR using decision rule described above but other efficacy (in particular duration of response), safety, and biomarker data will be considered as well. Novartis may decide to not expand the arm despite the efficacy probability threshold crossed.

With 20 treated patients, 5 or more responders need to be observed to meet the efficacy probabilistic threshold.

Part 2: Expansion Phase

If the pre-defined efficacy probabilistic threshold is met after the selection part, the arm 1A might be expanded.

A second interim analysis will be conducted including 20 additional patients treated in the expansion phase, i.e. based on the total of 40 patients. The objective of this second interim analysis is to support and inform decision-making on whether arm 1A will be: (1) further explored (2) stopped for futility. To determine whether arm 1A has the potential to demonstrate clinically meaningful ORR, an efficacy probabilistic threshold same as in part 1 will need to be crossed (see [Table 2-2](#)). If not, the arm 1A will be declared futile and further exploration/enrollment will be stopped in this combination. With 40 subjects at time of 2nd interim analysis treated in arm 1A (combining part 1 and part 2), 9 responders will have to be observed to cross the efficacy probabilistic threshold.

If efficacy probabilistic threshold is met at the 2nd interim analysis enrollment may continue in expansion up to approximately 80 subjects (i.e. 100 subjects in total adding the subjects in part 1).

After completion of the expansion phase, the following statistical hypothesis will be tested based on objective response rate (ORR) at time of primary analysis:

- H_0 : $ORR \leq 15\%$
- H_1 : $ORR > 15\%$

The null hypothesis will be formally rejected if the lower bound of exact 95% CI for ORR is above 15%. The primary analysis of ORR at the end of part 2 will be based on a combined pool of part 1 and part 2 data.

23 or more responses need to be observed among the 100 subjects to reject the null hypothesis. With those 23 responders among 100 subjects, the point estimate for ORR will be 23% with an exact 95% confidence interval of (15.2, 32.5).

2.5.3 Handling of missing values/censoring/discontinuations

For information on the handling of missing values/censoring/discontinuations, see the main SAP for the randomized part of the study.

2.5.4 Supportive analyses

Same supportive analysis on ORR using BIRC than the one described in the main SAP for the randomized part of the study will be performed for Arm 1A at 2nd interim analysis and primary analysis.

Concordance analysis of BOR

Refer to the main SAP for the randomized part of the study for details on the concordance analysis between BIRC assessment and local assessment.

Reasons for “Unknown” BOR

Reasons for “Unknown” BOR will be presented identically for the IAs and primary analysis. Therefore, more details on reasons for “Unknown” BOR can be found in the main SAP for the randomized part of the study.

Waterfall plot to depict anti-tumor activity

Waterfall plot to depict anti-tumor activity will be presented identically for the IAs and primary analysis. Therefore, more details on reasons for “Unknown” BOR can be found in the main SAP for the randomized part of the study.

Subgroup analyses

At primary analysis, data from part 2 will be combined with part 1 to assess ORR in the following subgroups :

- LDH (\leq ULN vs. $>$ ULN),
- ECOG PS (0 vs. 1).

2.6 Analysis of the key secondary objective

The key secondary objective of the study is to determine duration of response (DoR) treatment with spartalizumab in combination with LAG525 in subjects with previously treated unresectable or metastatic LAG3-positive melanoma. It will be analyzed at time of IAs, primary and final analysis.

When the main SAP for the randomized part of the study referred to the date of randomization for endpoints definition, the date of first study treatment dose is rather used for this arm 1A analysis.

2.6.1 Key secondary endpoint

For information on the key secondary endpoint, see the main SAP for the randomized part of the study. Note, due to small sample size at 1st interim analysis, only listings will be generated for DoR.

2.6.2 Statistical hypothesis, model, and method of analysis

For information on the statistical hypothesis, model, and method of analysis for the key secondary endpoint, see the main SAP for the randomized part of the study.

2.6.3 Handling of missing values/censoring/discontinuations

For information on the handling of the missing values/censoring/discontinuations for the key secondary endpoint, see the main SAP for the randomized part of the study.

2.6.4 Duration of follow-up

Study follow-up will be summarized as well as patient follow-up and will be defined as follows :

- Duration between the date of first dose of study treatment in arm 1A and data cut-off date = (Cut-off date - Date of first dose of study treatment in arm 1A+ 1) / 30.4375 (months),
- Duration between the date of first dose of study treatment in arm 1A and the last contact date = (Date of last contact/death date (equivalent to the date used for OS time) - Date of first dose of study treatment in arm 1A+ 1) / 30.4375 (months).

2.7 Analysis of secondary [REDACTED] efficacy objective(s)

The other secondary objectives are the following:

- Evaluate the efficacy of arm 1A, as measured by progression-free survival (PFS)
- Evaluate the efficacy of arm 1A, as measured by disease control rate (DCR)
- Evaluate the overall survival (OS) of arm 1A

2.7.1 Secondary [REDACTED] efficacy endpoints

For secondary endpoints definition, see the main SAP for the randomized part of the study.

Note, due to small sample size at 1st interim analysis, only listings for the following secondary endpoints PFS and OS will be provided. Full analyses using Kaplan Meier method will be performed at 2nd interim analysis, primary and final analyses.

2.7.2 Statistical hypothesis, model, and method of analysis

There will be no hypothesis testing for any of the endpoints listed above.

For the method of analysis of secondary [REDACTED] endpoints, refer to the main SAP for the randomized part of the study.

2.7.3 Handling of missing values/censoring/discontinuations

For handling of missing values/censoring/discontinuations for PFS and OS endpoints, please see the main SAP for the randomized part of the study.

2.8 Safety analyses

For all safety analyses, the safety set will be used. All listings and tables will include only arm 1A.

The overall observation period, incomplete dates, and safety assessments will be treated similarly in the IA analyses, the primary analysis and the final analysis. More details on these components of the safety analyses can be found in the main SAP for the randomized part of the study.

2.8.1 Adverse events (AEs)

Adverse event summaries and details will be presented identically for the IAs, the primary and the final analysis. Therefore, more details on AEs can be found in the main SAP for the randomized part of the study. Of note, the additional summaries to report all AEs, AEs related to study treatment, all SAEs, and SAEs related to study treatment as described in the main SAP for the randomized part of the study as “collected up to 150 days after last administration of PDR001/LAG525” will rather use the extended follow-up period definition ([section 2.1.1](#)).

2.8.1.1 Adverse events of special interest / grouping of AEs

Adverse events of special interest (AESI) during the on-treatment period will be tabulated. The list of AESI will also include relevant events for spartalizumab, and LAG525 agent.

Refer to the main SAP for the randomized part of the study for details on the analysis of AESIs. Of note, the additional summaries to report all AESIs as described in the main SAP for the randomized part of the study as “collected up to 150 days after last administration of PDR001/LAG525” will rather use the extended follow-up period definition ([section 2.1.1](#)). In addition, analysis of time to first occurrence summaries will not be generated.

2.8.2 Deaths

Deaths will be presented identically for the IAs, the primary and the final analysis. Therefore, more details on deaths can be found in the main SAP for the randomized part of the study. The additional summary reported all deaths “up to 150 days after last administration of PDR001/LAG525”, as described in the main SAP for the randomized part of the study, will rather use the extended follow-up definition ([section 2.1.1](#)).

2.8.3 Laboratory data

Grading of laboratory will be assigned programmatically as per National Cancer Institute (NCI) Common Terminology Criteria for Adverse Events (CTCAE) v5.0. The calculation of CTCAE grades will be based on the observed laboratory values only, clinical assessments will not be taken into account.

CTCAE Grade 0 will be assigned for all non-missing values not graded as 1 or higher. Grade 5 will not be used.

For laboratory tests where grades are not defined by CTCAE v5.0, results will be categorized as low/normal/high based on laboratory normal ranges.

Laboratory data summaries and listings will be presented identically for the IAs, the primary and the final analysis. More details on laboratory data summaries and listings can be found in the main SAP for the randomized part of the study.

For laboratory figures, only the eDish plot examining the relationship between peak total bilirubin (measured as the maximum post-baseline total bilirubin and maximum post-baseline alanine aminotransferase (ALT) (both in reference to the ULN) or maximum post-baseline aspartate aminotransferase (AST) will be produced at IAs, primary and final analysis.

Liver function parameters

The following liver function parameters are of interest : total bilirubin (TBL), alanine aminotransferase (ALT), aspartate aminotransferase (AST) and alkaline phosphatase (ALP). The number (%) of subjects with worst post-baseline values as per Novartis Liver Toxicity guidelines will be summarized.

The following summaries on peak post-baseline values will be produced:

- ALT >3xULN, ALT>5x ULN, ALT>10xULN, ALT>20xULN
- AST >3xULN, AST>5xULN, AST>10xULN, AST>20xULN
- ALT or AST > 3xULN, ALT or AST > 5xULN, ALT or AST > 8xULN, ALT or AST > 10xULN, ALT or AST > 20xULN
- TBL > 2xULN, TBL > 3xULN

For patients with AST and ALT \leq ULN at baseline:

- ALT or AST > 3xULN & TBL > 2xULN
- ALT or AST > 3xULN & TBL > 2xULN & (ALP < 2xULN or ALP \geq 2xULN)

For patients with ALT or AST > ULN at baseline

- Elevated ALT or AST (>3xULN if \leq ULN at baseline, or (>3xBsl or 8xULN) if >ULN at baseline)
 - o and TBIL (>2xBsl and 2xULN)
 - o and TBIL (>2xBsl and 2xULN) and ALP \geq 2xULN
 - o and TBIL (>2xBsl and 2xULN) and ALP < 2xULN

Potential Hy's Law events are defined as occurrence of AST or ALT > 3xULN and TBL > 2xULN, or occurrence of (ALT or AST >3xbaseline) OR (ALT or AST > 8.0xULN), whichever is lower, combined with (TBIL>2xbaseline AND >2.0xULN), for patients with abnormal ALT or AST baseline values; where combined elevations post-baseline are based on the peak values at any post-baseline time for a subject.

Further medical review has to be conducted to assess potential confounding factor such as, liver metastases, liver function at baseline etc.

2.11 Subject-reported outcomes

Not applicable

2.12 Biomarkers

2.12.1 Introduction

As a project standard, Novartis Oncology Biostatistics will analyze only biomarkers collected in the clinical database. The biomarker analysis covered within the SAP pertains mainly to the secondary objective endpoint of determining the proportion of subjects with a favorable biomarker profile (pFBP). More details on the pFBP can be found in the main SAP for the randomized part of the study.

2.12.2 Secondary biomarker objectives

Changes in phenotype and/or activation of T cell populations in the tumor and tumor microenvironment will be analyzed on an on-going basis as part of the secondary objective. Every effort will be made to make this data available for internal decision making purposes. Such analyses may include, but are not limited to number of CD8⁺ T cell infiltration, T cell activation level by IHC and gene expression analysis. T cell repertoire/clonality by TCR-sequencing is excluded from all interim analyses as well as beyond due to low assay success. Further discussions of the parameter definitions to support the biomarker objectives can be found in [Table 2-3](#) below.

Table 2-3 Parameter definitions for categorization of biomarker outcome at subject level

Biomarker parameter	Analysis	Criteria for favorable biomarker result
Number of tumor infiltrating T cells (TILs)	Changes of CD8 ⁺ T cell numbers as assessed by IHC in tumor/ tumor microenvironment with treatment	Increase
Activation level of TILs*	Change of T cell activation marker level(s) as assessed by IHC in tumor/tumor microenvironment with treatment	Increase
Changes in immune response gene expression signatures	Changes in expression of genes and/or gene signatures as assessed by mRNA analysis in tumor/tumor microenvironment with treatment	Defined per gene/gene signature

*Of note, the activation level of TILs by IHC (AQUA analysis) initially reported in the protocol may be excluded due to sample limitation associations with arm 1A, created by the need to retain tissue for potential further LAG3 test validation in support of future diagnostic development.

2.12.3 Biomarker data

As a project standard, Novartis Oncology Biostatistics will analyze only biomarkers collected in the clinical database. The biomarker analysis covered within the SAP pertains mainly to the secondary objective endpoint of determining the proportion of subjects with a favorable biomarker profile (pFBP). [REDACTED]

The biomarker analysis set, as it pertains to the secondary objectives consists of all subjects in the safety set with an evaluable baseline tumor biopsy sample. When evaluating the pFBP, the analysis set should include all subjects in the safety set with an evaluable baseline tumor biopsy sample and at least one post-baseline tumor biopsy sample with evaluable results for 2 or more biomarker parameters listed in Table 2-3 (paired biomarker analysis set).

Table 2-4 summarizes the biomarker collection schedules and sample types.

Table 2-4 Sample biomarker summary table

Biomarker parameter	Biomarker analysis measurement	Time point	Sample	Method	Dataset
Number of TILs	Percent of tumoral CD8+ cells	Screening Btw, C1D1 and C2D1*	Newly obtained tumor biopsy	IHC	B1
Changes gene expression signatures	T-cell Inflamed Signature (TIS) levels	Screening Btw, C1D1 and C2D1*	Newly obtained tumor biopsy	Nanostring	B1
Baseline LAG-3 expression (LAG525 treatment arm only)	Percent of tumoral LAG-3+ cells	Screening Btw, C1D1 and C2D1*	Newly obtained tumor biopsy	IHC	B1

2.12.4 General data handling and preprocessing

The mean of all pre dose assessments (i.e. screening and Cycle 1 Day 1 assessments) will be used as the baseline value. The on-treatment assessment will be the result from the tumor biopsy taken between C1D21 and C2D1.

When more than one biomarker data value are available for a subject at any time point, the mean of the replicate values will be used for all statistical analyses.

2.12.5 Secondary biomarker objectives

The secondary objective biomarker data will be listed for each subject for all time points (baseline and on treatment). Absolute and relative change (percent change or fold change, depending on biomarker) from baseline of each biomarker parameter will be calculated for each subject and summarized for arm 1A.

2.12.5.1 IHC for quantifying tumor infiltrating T cells (TILs)

The number of TILs at each timepoint will be assessed by measuring % CD8+ cells within the invasive margin, tumor and stroma area (as defined by Melamask staining).

For all CD8 parameters above, the baseline value, on-treatment (C1D21-C2D1) value, and the absolute difference from baseline to on-treatment will be listed for each individual subject for arm 1A. The mean, standard deviation, %CV, median, minimum, maximum, inter-quartile range and number for all subjects (regardless of treatment arms) will be reported for baseline and change from baseline to on-treatment by combination arm. Inter-quartile range is the number of data points between the 25th and 75th percentile.

The summary statistics : mean, standard deviation, %CV, median, minimum, maximum, inter-quartile range for baseline %CD8+ cells will be summarized for patients with best overall response of CR or PR (e.g. responders) versus others.

For all parameters above, the baseline value, on-treatment value, and the absolute difference from baseline to 3-4 weeks will be listed for each individual subject. The mean, standard deviation, %CV, median, minimum, maximum, inter-quartile range and number for all subjects (regardless of treatment arms) will be reported for baseline and change from baseline to on-treatment (C1D21-C2D1). Inter-quartile range is the number of data points between the 25th and 75th percentile.

2.12.5.2 Nanostring for quantifying gene expression signatures

The Tcell inflamed signature will be assess by the T-cell Inflammed Signature (TIS) score for Nanostring data.

For TIS score, the baseline value, on-treatment (C1D21-C2D1) value, and the fold change (on-treatment / baseline) will be listed for each individual subject. The mean, standard deviation, %CV, median, minimum, maximum, inter-quartile range and number for all subjects (regardless of treatment arms) will be reported for baseline and fold change (on-treatment / baseline). Inter-quartile range is the number of data points between the 25th and 75th percentile.

The summary statistics : mean, standard deviation, %CV, median, minimum, maximum, inter-quartile range for baseline TIS score will be summarized for patients with best overall response of CR or PR (e.g. responders) versus others.

2.12.5.3 Calculation of pFBP

The biomarkers listed in [Table 2-3](#) will be used to calculate the proportion of subjects with a favorable biomarker profile (pFBP).

For each biomarker involved in the evaluation of pFBP as stated above, the baseline, 3-4 weeks biomarker values, and the absolute difference from baseline to 3-4 weeks will be listed for each individual subject by combination arm. The mean, standard deviation, %CV, median, minimum, maximum, inter-quartile range and number for all subjects (regardless of treatment arms) will be reported for baseline and change from baseline to 3-4 weeks by combination arm. Inter-quartile range is the number of data points between the 25th and 75th percentile.

If an individual subject has two favorable biomarker parameters from Table 2-3 then that subject will be considered to have a favorable biomarker profile. A favorable biomarker will be defined as follows:

Number of tumor infiltrating T cells (TIL) as measured by CD8 IHC:

- An increase from baseline to on-treatment (C1D21-C2D1) in the IE CD8+ density is considered a favorable change as follows:
 - IE CD8 increase which is $\geq 1\%$ in magnitude (i.e. [on-treatment C1D21-C2D1 %IE value] – [baseline IE value] = $\geq 1\%$)

And

- Percent fold change in IE is $\geq 30\%$ (i.e. ([on-treatment C1D21-C2D1 %IE value] – [baseline IE value])/[baseline IE value] = $\geq 30\%$)

Changes in immune response gene expression signature as measured by Nanostring:

- For baseline to on-treatment changes in the TIS score, the following would be considered favorable:
 - ≥ 1.5 fold change (i.e. on-treatment aggregate gene signature score)/[baseline aggregate gene signature score]

For each combination arm, the proportion of subjects with a favorable biomarker profile (pFBP) are then defined as the number of subjects with favorable biomarker profiles divided by the number of subjects enrolled into the arm which are included in the paired biomarker analysis set for that particular interim analysis and will be summarized.

[REDACTED]

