2.12.5.3 Nanostring for quantifying gene expression signatures

Gene expression data will be calculated using the following variables provided in the raw data:

- raw gene expression
- housekeeper-gene normalized gene expression

The gene signatures that will be scored for expression are defined in [Table 2-20](#). The score of each gene signature will be calculated using the simple average of log expression values for all genes. The aggregate score for the three gene signatures, calculated as average of the score of each gene signature will be used as one of the criteria for favorable biomarker result. Additional genes may be considered for gene expression analyses pertaining to biomarker outcomes.

Table 2-20 Immune response gene expression signatures

Signature	Gene names									
T-cell inflamed [Ayers, 2017]	CD3D	IDO1	CIITA	CD3E	CCL5	GZMK	CD2	HLA-DRA	CXCL13	IL2RG
	NKG7	HLA-E	CXCR6	LAG3	TAGAP	CXCL10	STAT1	GZMB		
CD8 T-cell	CCL5	CTSW	FASLG	CD8B	ZNF683	GZMA	XCL2	CD7	KLRC1	CD8A
	XCL1	TRDC	NKG7	KLRK1	GNLY	PRF1	GZMB	GZMH	LAG3	KLRD1
IFN-gamma	IFNG	CXCL9	CXCL10	CXCL11	GBP1					

For all parameters above, the baseline value, on-treatment (C1D21-C2D1) value, and the difference from baseline to 3-4 weeks will be listed for each individual patient by treatment arm. The mean, standard deviation, %CV, median, minimum, maximum, inter-quartile range and number for all patients (regardless of treatment arms) will be reported for baseline and change from baseline to on-treatment by combination arm. Inter-quartile range is the number of data points between the 25th and 75th percentile. Calculation of proportion of patients with favorable biomarker profile

The biomarkers listed in [Table 2-20](#) will be used to calculate the proportion of subjects with a favorable biomarker profile (pFBP).

- As for the parameter of number of tumor infiltrating T cells (TIL), an increase from baseline to on-treatment (C1D21-C2D1) in the IE CD8+ density is considered a favorable change. Whether such increases are accompanied by a decrease in IST CD8+ density may be taken into consideration as a signal for CD8+ T cell migration into the tumor. Furthermore increases in CD8+ density in IST areas closer to the IE-IST border (e.g. an increase in 0-10 μm and >10-20 μm regions compared to more distal regions, >30 μm) may be taken into consideration as another signal for CD8+ T cell migration into the tumor

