- As for the activation level of TIL, an increase from baseline to on-treatment in percentage of GzmB+ T cells is considered favorable. In the presence or absence of an increase in GzmB+ T cells, an increase in percentage of Ki67+ T cells is also considered favorable. If decreases in both GzmB + T cells and Ki67+ T cell are observed, this parameter would not be considered favorable.

- As for the TIL repertoire/specificity of T cell response to tumor, an increase from baseline to on-treatment in TCR clonality is considered favorable.
- An increase from baseline to on-treatment in the aggregate gene signature score would be considered favorable.

For each biomarker involved in the evaluation of pFBP as stated above, the baseline, 3-4 weeks biomarker values, and the difference from baseline to 3-4 weeks will be listed for each individual patient by combination arm. The mean, standard deviation, %CV, median, minimum, maximum, inter-quartile range and number for all patients (regardless of treatment arms) will be reported for baseline and change from baseline to 3-4 weeks by combination arm. Inter-quartile range is the number of data points between the 25th and 75th percentile.

If an individual subject has two or more favorable biomarker parameters from [Table 2-16](#) then that subject will be considered to have a favorable biomarker profile.

For each combination arm, the proportion of subjects with a favorable biomarker profile (pFBP) are then defined as the number of subjects with favorable biomarker profiles divided by the number of subjects enrolled into the arm which are included in the biomarker analysis set for that particular interim analysis and will be summarized.

[REDACTED]

[REDACTED]

[REDACTED]

[REDACTED]

[REDACTED]

[REDACTED]

[REDACTED]

[REDACTED]

[REDACTED]

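### Arm 1A calls a gene-score ratio of 1.5 a fold change, but the only score definition given is a log average, so the threshold moves with baseline and normalization

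*SAP*

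**What the plan says.** The Arm 1A SAP, section 2.12.5.3, introduces its gene-expression criterion as a change in the TIS score. It then sets the cut-off as at least "1.5 fold change (i.e. on-treatment aggregate gene signature score)/[baseline aggregate gene signature score". Section 2.12.5.2 of the same SAP uses the same form for reporting TIS: "the fold change (on-treatment / baseline) will be listed for each individual subject", with summary statistics on that ratio.

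Neither section says on what scale the score is expressed. Section 2.12.1 of the Arm 1A SAP sends the reader elsewhere: "More details on the pFBP can be found in the main SAP for the randomized part of the study".

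The main SAP, section 2.12.5.3, does define the scores. It starts from raw expression and "housekeeper-gene normalized gene expression", and continues: "The score of each gene signature will be calculated using the simple average of log expression values for all genes". The T-cell inflamed signature is one of the three signatures in its Table 2-20. The combined measure is "The aggregate score for the three gene signatures, calculated as average of the score of each gene signature". The main SAP's own criterion is directional only: "An increase from baseline to on-treatment in the aggregate gene signature score would be considered favorable".

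In Arm 1A a subject has a favorable profile when two parameters are favorable. TCR clonality has been dropped, and section 2.12.2 adds that "the activation level of TILs by IHC (AQUA analysis) initially reported in the protocol may be excluded due to sample limitation". Section 2.12.5.3 spells out favorable criteria for two parameters only: CD8 by IHC and this gene score.

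**The concern.** A difference of two log averages is the log of the fold change in geometric-mean expression. A ratio of two log averages has no such meaning. It depends on where the baseline lies and on any constant by which expression was normalized. The main SAP's rule, any increase in score, is sound on a log scale. The Arm 1A SAP replaces it with a ratio and a numerical cut-off, using the main SAP's term for the score and mentioning no back-transformation.

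A programmer who follows the text would divide log averages. Two subjects with the same relative rise in expression could then be classed differently because their baselines differ. If the activation assay is not run, a favorable profile requires both CD8 and this score, so any misclassification here passes directly into pFBP. The TIS summaries in section 2.12.5.2 would carry the same problem.

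**Working it through.** The 1.5 is a chosen threshold with no inputs behind it, so there is no plan figure to reproduce. The check is what the threshold means on the only scale that the documents define.

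**Inputs.** The score S is a mean of log expression (main SAP 2.12.5.3; log base not stated). The rule is S_on / S_base ≥ 1.5 (Arm 1A SAP 2.12.5.3). The baselines below are assumptions on a log2 scale, because neither SAP gives a score value.

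**Step 1: positive baseline b.** The true fold change in geometric-mean expression is 2^(S_on − b). The rule requires S_on ≥ 1.5b, so S_on − b ≥ 0.5b, and the fold change needed is 2^(0.5b). For comparison, a true 1.5-fold rise adds log2(1.5) = 0.585 and gives the ratio (b + 0.585)/b.

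| Assumed baseline b | Score needed (1.5b) | True fold change needed, 2^(0.5b) | Ratio from a true 1.5-fold rise |
|---|---|---|---|
| 0.5 | 0.75 | 1.19 | 2.17 |
| 1 | 1.5 | 1.41 | 1.585 |
| 2 | 3 | 2 | 1.292 |
| 4 | 6 | 4 | 1.146 |
| 6 | 9 | 8 | 1.097 |
| 8 | 12 | 16 | 1.073 |

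The ratio rule matches a true 1.5-fold change at one baseline only: 0.5b = 0.585, so b = 1.17. Below that it is more lenient; above it, stricter.

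**Step 2: normalization.** The same 2-fold rise in expression, rescaled by a constant (log base cancels in the ratio):

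- 4 to 8: log 8 / log 4 = 1.50, passes.
- 40 to 80: log 80 / log 40 = 1.19, fails.
- 400 to 800: log 800 / log 400 = 1.12, fails.

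**Step 3: negative baseline.** If b < 0, the inequality becomes S_on ≤ 1.5b, which is a decrease. From −2 to −3 the ratio is 1.5 (favorable) although expression has halved. From −2 to −1 the ratio is 0.5 (not favorable) although expression has doubled. This needs baseline scores below zero, that is, geometric-mean normalized expression below 1. The documents neither show nor exclude that.

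**Step 4: which score.** Arm 1A SAP 2.12.5.3 names TIS and then divides the aggregate score. In the main SAP these differ: one signature against the mean of three. Table 2-4 of the Arm 1A SAP lists TIS alone. The same section 2.12.5.3 lists an absolute difference from baseline for each pFBP biomarker, while section 2.12.5.2 lists a ratio for TIS.

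**The case against.** The strongest reply is that the log scale is inferred. Sections 2.12.5.2 and 2.12.5.3 of the Arm 1A SAP never say that the TIS score is logged. That SAP also replaces much of the main SAP's scheme: one signature instead of three, and numerical cut-offs instead of any increase. Its section 2.12.5 allows a percent or fold change depending on the biomarker, so the ratio may be a deliberate choice for a linear-scale TIS score, for which it would be an ordinary fold change. This stands as a limit on the point: a reader cannot conclude that the sponsor certainly intended to divide log scores. It does not remove the defect. The text uses the main SAP's term, the cross-reference leads to a log definition, and no linear scale is stated anywhere.

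Three stronger readings should not be drawn.

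- **That the rule reverses direction.** It does so only with negative baseline scores, and listing housekeeper normalization as an input does not establish these.
- **That the plan in effect demands a 4- or 16-fold rise.** Those figures depend on assumed baselines; at a baseline of 1 the requirement is 1.41-fold, close to 1.5.
- **That this criterion alone decides pFBP.** If only CD8 and the gene score remain, the CD8 criterion is equally necessary. Exclusion of the activation assay is stated only as a possibility, and Table 2-3 still lists that parameter.

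The planned listing of absolute differences also means that, for logged scores, the correct quantity would already be available. What would remain wrong is the favorable/unfavorable classification and the ratio summaries.

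**Conclusion.** The concern holds in this form: the Arm 1A SAP fixes a ratio criterion for a score whose only definition in the documents is logarithmic, and it uses two different names for that score within one criterion. On that definition, the change needed to pass varies with baseline and normalization: about 1.4-fold, 2-fold, 4-fold and 16-fold at assumed log2 baselines of 1, 2, 4 and 8. That the threshold varies follows from the log definition for any log base; the particular fold values rest on the assumed baselines.

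The consequence is limited. pFBP is a secondary proportion that is summarized without a test. Under section 2.5.2 of the Arm 1A SAP, expansion rests primarily on observed ORR, with biomarker data considered as well. The ORR analysis is unaffected. The rule should still be corrected, because it can misclassify subjects on a named secondary endpoint.

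**What to change.** In Arm 1A SAP 2.12.5.3, name one score, TIS or the three-signature aggregate, and state its scale, its log base and the normalization applied.

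- **If it is the log average of the main SAP:** define favorable as on-treatment minus baseline score of at least log(1.5), which is 0.585 for log2, 0.405 for natural log and 0.176 for log10. Equivalently, back-transform both scores before taking the ratio. Change section 2.12.5.2 to summarize the difference or its antilog.
- **If a linear-scale TIS score is meant:** say so, define it, and keep the ratio in both sections. The 0.585 cut-off must not be applied to a linear score.

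The cost is a few lines of SAP text and one derivation. No new data or assays are needed.
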